Patient Priorities Care requires the elicitation and documentation of patient health outcome goals and care preferences and the alignment of clinical care with goals and priorities to achieve patients' health outcome goals and reduce the burden of multi-morbidity. Participants will be enrolled in the Patient Priorities Care Program and speak with a trained health priorities facilitator to elicit their healthcare preferences and health outcome goals, which together constitute their health priorities. This information will be documented, entered into the EHR, and shared with the clinicians who will then use the Patient Priorities Care approach with patients to inform and guide treatment decisions. Patients will participate in the program and be followed for up to one year from the health priorities identification visit.

Sample

Patients: Potentially eligible participants for this project include Medicare beneficiaries (Traditional, Medicare Advantage, and dual eligible) 66 years or older who are patients of participating clinicians.

We assessed the power to detect clinically relevant differences in Patient-Reported Outcomes (PROs) and categories of healthcare utilization, both needed to measure value. We calculated minimal detectable differences for the primary PPC outcomes based on a sample size of 500 participants (250 PPC and 250 in UC) that assumed 80% power, a one-tailed alpha of 0.05, and an R-squared of 0.2 from other covariates. Assuming a standard deviation of 24.1 at pre-test and 17.6 at post-test and a correlation between measurement pairs of 0.55 (based on pilot data) allows us to detect a between-group difference in mean change in the TBQ score from pre-test to post-test of -4.6 points.³⁷ Comparing the PPC group to the UC care group, our sample permits us to detect an odds ratio of 1.7 with respect to discontinuing medications and an odds ratio of 0.52 with respect to having diagnostic tests ordered.³⁸

Inclusion/Exclusion Criteria

The evaluation of PPC in the clinical practice will take place as part of the patient's ongoing healthcare, and is minimal risk. Criteria for inclusion in the clinical program will be expansive in order to offer the opportunity for the largest number of reachable patients possible. All recruits will be those who are currently patients at Cleveland Clinic. Patient's meeting any of the exclusion criteria will not be approached by the Cleveland Clinic clinicians.

Inclusion Criteria:

1. Age 66 and older

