Clinical Procedures				Goal Facilitation Visit(s)	PPC Clinician Visit(s)	Goal Facilitator Follow up		
Research Procedures		Pre-Screening	Baseline Interview				Follow up interview	Follow up
	Week	Up to -7	-5 to 0	-6 to -1	0	2 to 6 (1-2wk after 1 st PCP)	34 to 52	Up to 52
	Month		-1	-1	0	1-2	8 – 12	12
Intervention arm	Consent		x				x	
	EHR data extraction		x					x
	Identification/ discussion of patient health priorities			x	x	x		

	Interview 
 • Demographics • 5-word recall* • PROMIS • CollaboRATE • Tx Burden questionnaire 		x					x	
	PCP visit			x					
Usual care arm	Interview 
 • Demographics • 5-word recall* • PROMIS • CollaboRATE • Tx Burden questionnaire 		x				x		
	PCP visit				x		x	x	
	EHR data extraction		x						x

*Baseline in-person interview only.

Patients meeting criteria within the Cleveland Clinic Lakewood Family Health Center (FHC) and Brunswick FHC patients who are scheduled to have visit during study period will be recruited using mail, or My Chart message about the project taking place. Lakewood FHC will be serving as intervention site and Brunswick FHC as usual care. Eligible and consented patients will participate in the program and be followed for up to one year from the goal elicitation visit. Primary physicians, and priorities facilitators (i.e. Geriatrician, MAs, Care Coordinators, Patient Liaison Program Coordinators, and Nurse practitioners) will undergo training and preparation to elicit and provide care aligned with health priorities. This training has been developed and tested during the Yale University pilot study of Patient Priorities care.

Pre-screening and Recruitment (Research procedure)

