A list of patients meeting above criteria will be generated by the methods described below, and provided to PCPs to obtain their permission to invite patients. PCPs may suggest removing any patients who may not be appropriate for the intervention at PCP's discretion. Research team will conduct a baseline interview after obtaining verbal consent from the patients. Priorities Facilitators will be notified to invite these patients to have their health priorities identified and their care aligned with these priorities. To maximize flexibility and align with current workflow, the invitation for priorities identification can be during a regular visit, by phone, by mail, or other means already used by the practices (e.g. same visit as invitation; part of annual wellness visit, etc.).

Project specific generated list: Each week, a scheduling system will provide an automated list of targeted patients with appointments 6 weeks later. Appointment types include in-person office visit, distance health, virtual, or telephone visit. This system is linked with EHR and widely used at our institution. Once target patients are identified and approved by the PCP, research personnel will contact via mail, or My Chart messaging to introduce the Patient Priorities Care program with an information sheet to explain the Patient Priorities Care process and ask them to contact the research team if they want to opt out. Opt-out patients will be recorded in the screening log to avoid contacting again for future recruitment.

Care providers referral: Care providers can make a referral if they have patients who could benefit from the Patient Priorities Care program, otherwise meet inclusion and exclusion criteria, and have regular visits in next few months. Care providers can discuss the program and provide information sheet to the potential participants. Clinician will notify the research team of the potential patients who have agreed to participate in the PPC. Research team will contact these potential participants to obtain consent to participate in Patient Priorities Care before asking any research questions. Care providers will also notify names of patients who decline to participate in order to avoid contacting the same patients again for future recruitment.

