Primary Care Coordination patients list: For patients enrolled through the Care Coordination program, research personnel will identify the individuals ahead of time and obtain permission from their PCPs. Research team will contact via mail, or My Chart messaging to introduce the Patient Priorities Care program with an information sheet to explain the Patient Priorities Care process and ask them to contact research team if they want to opt out. After excluding patients who opted out, research personnel will contact patients to obtain consent and conduct baseline interview. Because this project provides prioritized patients' list based on their existing Care Coordination patient list for the Coordinators to reach out, this process adds very little burden on Care Coordinator's part.

Usual care Group

Concurrent to the Patient Priorities Care implementation, we will begin to identify the usual care group which will include up to 250 patients. We will identify a sample similar to the intervention group, using the same inclusion/exclusion criteria and clinical judgment. The usual care group will be identified from Brunswick FHC patients.

The usual care group will be identified through the same electronic health record search and Care Coordination patient list described above, and PCPs will have the option of not including any of their patients for interview for usual care group.

The usual care group during the study period will receive a recruitment letter from their clinician

describing the research and interview. Patients will be able to opt-out if they do not wish to be contacted by contacting research team listed in the invitation letter. For patients who do not opt-out, a centralized, trained research personnel will contact candidates by phone to confirm eligibility and to obtain verbal consent for enrollment in the usual care arm which involves standard clinical care, data collection through an interview, and a medical record review.

Consent process

We will require a full waiver of consent and HIPAA authorization for the health care utilization data that will be used as part of the screening process and evaluation of the patient population. We will also request a waiver of signed consent and HIPAA authorization for participation of clinicians and patients in the research evaluation. It would be impractical to gain signed consent for this information, specifically for this population and the research involves minimal risk.

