Consent process will be conducted primarily over the phone by a trained project staff member. Patients will be notified via letter, My Chart message or phone that a CCF research personnel will be contacting them to conduct the interviews. A trained research coordinator will administer the qualitative survey. Participants in both intervention and usual care groups will receive \$10 for each research interview for a total reimbursement of up to \$20.

Baseline interview

Once potential patients are identified, research personnel will add participants' contact information into a secure electronic data collection system (REDCap) which the research team will also use to contact the participants to administer the interview. Up to 6 weeks prior to their next PCP appointment, selected patients will be contacted by phone or in-person to confirm consent to participate. Once eligibility is confirmed, research personnel conduct phone or in-person baseline interview whichever is preferred by the patient. Baseline interview could follow after Priorities Facilitators (Geriatrician, MA, Care coordinator, Patient Liaison Program Coordinators, Nurse Practitioners) completes priorities identification process. This can be done before or the day of the initial PCP visit to begin deciding treatment plans based on priorities. Contact information will be stored separately from interview and medical record data and destroyed once the follow-up interviews have been conducted and data collection and cleaning is complete.

Priorities Facilitators will help patients identify their health priorities, complete the health priorities template in EHR. Please note that similar process has been routinely done at the clinic as part of Care Coordinators' and Patient Liaison Program Coordinators' job (Appendix 1), and this project provides more structure in documentation and collaboration with other care providers involved.

PCPs will be asked to review the patients' health priorities at subsequent clinical follow up visits and update if necessary.

At the intervention site, we will identify site champions to develop continued buy-in from providers (e.g., staff meetings, individual meetings, case examples), obtain feedback, and notify the PI and research team of unanticipated problems.

Intervention (Clinical procedure)

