Patient Priorities Care is an innovative approach to shared decision-making that draws from existing professional training (e.g. clinical competencies, motivational interviewing, and geriatrics care). Patient Priorities Care requires the elicitation and documentation of patient health outcome goals and care preferences and the alignment of clinical care with health goals and healthcare preferences (collectively referred to as health priorities) Participants will be enrolled in the Patient Priorities Care Program and communicate with a trained priorities facilitator in-person or over the phone to elicit their health priorities. This information will be documented in the PPC- GOALS AND PREFERENCES form in the EHR and shared with the clinicians who will then use the Patient Priorities Care approach with patients to inform and guide treatment decisions.

Patients will participate in the program and be followed for up to one year from the priorities elicitation visit by the research team. The target follow-up time is 8-10 months. The PCPs will be trained in decisional strategies that have been shown to help align care with patients' health priorities. While encouraged to use these decisional strategies, PCPs will be free to make the recommendations they feel most appropriate for each patient.

This intervention has been developed to be integrated seamlessly into usual care, and does not involve any research aspect such as program development, data collection, and evaluation at all. Documentation completed by Facilitators is considered part of standard clinical care. Intervention development, data collection and evaluation including follow up data collection are conducted by the research team. What PCPs and facilitators are asked to perform for this project is within their standard scope of work. The intervention does not require additional visits or substantially increased provider time for PCPs as the Goals and Preferences information collected by the Facilitator will be used as decision aid during regular office visits. However, it is to the providers' discretion, to spend as much time as needed if that would benefit the participating patient.

Priorities Facilitators

The Priorities Facilitators will be trained health professional (i.e. Geriatrician, MA, Care Coordinators, and Patient Liaison Program Coordinators, Nurse practitioners).

Responsibilities

1. Undergo training and preparation to elicit and document patients' health priorities

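### The protocol lets the PPC-arm baseline interview follow priorities facilitation, so some baseline scores used for adjustment can be partly post-treatment; size and direction of any bias are unknown

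*Protocol*

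**What the plan says.** **Order of the two steps.** The Protocol describes it in three places.

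- Pre-screening and Recruitment puts the interview first: "Research team will conduct a baseline interview after obtaining verbal consent from the patients. Priorities Facilitators will be notified to invite these patients".
- Baseline interview permits the reverse: "Baseline interview could follow after Priorities Facilitators (Geriatrician, MA, Care coordinator, Patient Liaison Program Coordinators, Nurse Practitioners) completes priorities identification process". It sets no limit on how many patients this may apply to. The next sentence reads "This can be done before or the day of the initial PCP visit to begin deciding treatment plans based on priorities". Its subject could be the interview or the facilitation, and no order is set within the day of the visit.
- Table 1 places the baseline interview in weeks -5 to 0 and the goal facilitation visit in weeks -6 to -1. The intervention-arm row "Identification/ discussion of patient health priorities" is marked from the facilitation visit onward. These windows overlap and allow either order.

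**What facilitation is.** The Intervention section says "Patient Priorities Care requires the elicitation and documentation of patient health outcome goals and care preferences", and of the result, "This information will be documented in the PPC- GOALS AND PREFERENCES form in the EHR". The Usual care Group section describes "enrollment in the usual care arm which involves standard clinical care, data collection through an interview, and a medical record review", with no facilitation step.

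**Use of the baseline score.** The Protocol's Data Analysis section and the SAP's Multivariate models section both adjust follow-up outcomes for the baseline outcome value. Neither document plans to record the order of interview and facilitation, or to examine its effect.

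**The concern.** Baseline adjustment assumes that the covariate was measured before treatment could affect it. If a PPC patient has already had a structured conversation about goals and care preferences, the baseline score may carry part of the intervention's effect. By design that can happen in the PPC arm only.

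If facilitation has already improved the score, adjustment removes part of the PPC effect. If it makes patients more aware of burden, so that they report more of it, adjustment exaggerates the effect.

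The outcomes exposed are those scored at interview: TBQ, CollaboRATE and PROMIS. The Protocol names PROMIS-10 at baseline and the SAP names the Social Roles and Activities form; the point applies to whichever is asked. CollaboRATE may be the most exposed, because it asks whether care was collaborative and goal-focused. Nonhealthy days is not an interview score and is outside this point.

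**Working it through.** **Inputs.** The Protocol's Sample section gives the TBQ inputs: "Assuming a standard deviation of 24.1 at pre-test and 17.6 at post-test and a correlation between measurement pairs of 0.55". It also gives 250 per arm, 80% power, one-tailed alpha 0.05 and a detectable difference of 4.6 points. The SAP's Setting and Population section gives 125 per site.

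**The plan's own figure.**
- SD of change = sqrt(24.1² + 17.6² − 2 × 0.55 × 24.1 × 17.6) = 20.59.
- Detectable difference = (1.645 + 0.842) × 20.59 × sqrt(2/250) = 4.58, which rounds to the stated 4.6.
- This match does not apply the stated R-squared of 0.2. Applying it gives 4.58 × sqrt(0.8) = 4.10. That is a separate matter and does not affect what follows.

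**How a baseline shift enters the estimate.** The adjusted difference is the follow-up mean difference minus slope × the baseline mean difference. If facilitation moves the PPC baseline mean by m points, the estimate moves by −slope × m. Here m = (share of late interviews) × (mean shift among those patients).
- Slope = 0.55 × 17.6 / 24.1 = 0.402.
- Adjusted SE at 125 per arm = 17.6 × sqrt(1 − 0.55²) × sqrt(2/125) = 1.86. This ignores the propensity weights and other covariates.

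**Illustration.** The values of m are assumed; none comes from the documents.

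| Shift in PPC baseline mean (points, either sign) | Bias (points) | Bias / SE |
|---|---|---|
| 0.1 | 0.04 | 0.02 |
| 1.0 | 0.40 | 0.22 |
| 2.5 | 1.00 | 0.54 |
| 5.0 | 2.01 | 1.08 |

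Coverage of a 95% interval with a bias of d SEs is Φ(1.96 − d) − Φ(−1.96 − d). It is 95.0% at d = 0.02 and Φ(0.88) − Φ(−3.04) = 80.9% at d = 1.08.

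The slope applies to TBQ only. CollaboRATE is dichotomised and analysed by logistic regression, and the documents give no inputs for it or for PROMIS.

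**What the sensitivity analyses can do.** This was simulated with 4,000 trials, 125 per arm, a true effect of −4.6, half the PPC baselines late at random, and late scores carrying half the effect. There were no propensity weights. The mean shift is 0.5 × 0.5 × 4.6 = 1.15 points, so the expected bias is 0.402 × 1.15 = 0.46.

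| Analysis | Mean estimate | SD |
|---|---|---|
| As planned | −4.14 | 1.87 |
| PPC arm restricted to on-time interviews | −4.61 | 2.30 |
| Late baselines set to missing and imputed | −4.61 | 2.02 |

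With the shift reversed, the planned analysis gave −5.04 and the other two −4.59. Both checks recover the effect only because lateness is random here.

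**Precision cost of restriction.** SE ratio = sqrt((1/(1 − q) + 1)/2), where q is the share late. At q = 0.25 it is 1.08 (SE 2.01); at q = 0.5 it is 1.22 (SE 2.28).

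**The case against.** The strongest reply is that no harm is shown. Nothing in the documents establishes that any interview was late or that facilitation moves any score. Clinicians have generally not yet acted on the priorities at that stage, and the SAP calls the research exploratory. All of this stands, and it lowers the severity. It does not make a post-facilitation score a pre-treatment one.

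The contrast between arms may also be less sharp than the design suggests. The Baseline interview section says a similar process was already routine for Care Coordinators, Appendix 1 maps their job to priority assessment, and usual care patients come partly from the Care Coordination list. Some may have had comparable contact. The Protocol does not say whether the routine process extends to the usual care site, so this stays open. It also describes PPC as adding structure to that process.

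The checks have limited power. In the simulated case the planned analysis has root mean squared error sqrt(0.46² + 1.87²) = 1.93, against about 2.02 (imputed) and 2.30 (restricted). If every PPC baseline was late, neither check can run. This is why the planned analysis should stay primary and why the count of late interviews is the most useful output.

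A reader might infer that Table 1 contradicts the permission for a late interview. It does not, since its windows allow both orders. The tension is between the two text sections.

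**Conclusion.** The point holds at minor to moderate weight. The plan as written permits a partly post-treatment baseline in the PPC arm, uses that baseline for adjustment, and has no step to detect or examine it.

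For TBQ, about 40% of any shift in the PPC baseline mean reaches the adjusted estimate. Assumed mean shifts of 0.1 to 5 points give 0.04 to 2.0 points, or about 0.02 to 1.1 SE at 125 per arm. This rests on the Protocol's pilot SDs and correlation, a linear unweighted model, and shifts that are assumptions only.

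Two stronger readings are tempting, and the documents support neither. One is that the PPC effect is biased toward the null: the sign depends on whether facilitation lowers or raises reported scores, which is not given. The other is that the bias can be capped at some small fraction of a standard error: any such cap comes from the values chosen for the share late and the shift, and the documents set no upper limit.

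**What to change.** Enrolment is very probably closed. The Protocol's Follow up data collection section refers to a problem with follow-up interviews reported in July 2021, and the 2024 SAP speaks of sample size in the past tense. In that case:

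1. Keep the planned analysis as primary.
2. Extract the date on which the EHR goals-and-preferences form was first completed, or an earlier recorded facilitation contact. Compare it with the baseline interview date and report how many interviews fell before, on the same day and after. Show same-day cases separately, because no order is set within the day.
3. If any are late, do not describe those values as pre-treatment. For each interview-based outcome, add a sensitivity analysis that either sets late baselines to missing and imputes them with the planned procedure, or restricts the PPC arm to on-time interviews with weights re-estimated. Label it post hoc if outcomes have already been analysed.
4. If too few are on time, state as a limitation that bias may run in either direction.

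If enrolment is still open, reconcile the Pre-screening and Recruitment and Baseline interview sections so that the research interview precedes the first facilitation contact.

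**Cost.** The facilitation date is not in the Protocol's data extraction list, so a small extra extraction is needed before de-identified transfer. If no interview was late, that check closes the matter. Restriction raises the SE by about 8% at 25% late and 22% at 50% late, and may introduce selection, since who was facilitated first may not be random. Imputation also relies on lateness being unrelated to outcome, given the variables in the imputation model. If enrolment is open, requiring the interview before facilitation gives up some of the workflow flexibility that the Protocol seeks.
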